9.0 MONITORING UNTOWARD EFFECTS ASSOCIATED WITH OR RESULTING FROM STUDY

Site research staff must first follow both the UNC IRB and their own IRB's procedure for reporting and managing untoward effects.

There are three types of untoward effects to be identified: 1) those related to the participant, 2) those related to the study staff, and 3) those related to the neighborhood/community (*if applicable*).

First, the study will catalogue any untoward effect related to the participant. Reporting is required for occurrences including social harms, psychological distress, and serious life-threatening events such as suicide attempts. These may be immediately apparent to the study staff, such as the participant's emotional upset state requiring referral for counseling; or they may be delayed and reported later to study staff, such as physical harm to an individual for having participated in the study. Study staff will notify the protocol team of these untoward effects using the iTech query notification system (QNS) accessible through the iTech website (<https://itechnetwork.org>). Study staff will complete CRFs to further document adverse events and social harms. Study staff will be briefed during the training on the scope of possible untoward effects and instructed to report events.

Second, study staff may encounter untoward events during sessions that personally affect them. Training and guidance will seek to minimize this risk. Nonetheless, an assessment of the cost of conducting this study must include cataloguing these events as well. The protocol chairs should be

notified of these events so that they may be immediately addressed, evaluated, and guidance modified or expanded to minimize similar risk to other study staff.

Third, a critically important area any community-based study intends to evaluate is the impact, including untoward effects, of the project on the community. This will be done informally for this protocol with untoward events being reported to the protocol team.

All untoward effects/adverse events/unanticipated problems will also need to be reported to the UNC IRB if they meet all three of the following criteria:

“Unanticipated problems involving risks to subjects or others” (UPIRSO) refers to any incident, experience, or outcome that:

- 1) is unexpected (in terms of nature, severity, or frequency) given (a) the research procedures that are described in the protocol-related documents, such as the IRB-approved research protocol and informed consent document; and (b) the characteristics of the subject population being studied;
- 2) is related or possibly related to a subject’s participation in the research; and
- 3) Suggests that the research places subjects or others at a greater risk of harm (including physical, psychological, economic, or social harm) than was previously known or recognized.

Events that meet the criteria for an UPIRSO and are also serious adverse events should be reported to the UNC IRB within one (1) week of the investigator becoming aware of the event. Any other events that meet the criteria for a UPIRSO should be reported to the IRB within two (2) weeks of the investigator becoming aware of the problem.

If the report cannot be completed in its entirety within the required time period, a preliminary report should be submitted. The report should be amended once the event is resolved and/or more information becomes available.

10.0 STATISTICAL/ANALYTIC CONSIDERATIONS

10.1 Introduction

10.1.1 Usability Testing Overview

We will conduct usability testing with 8-12 YMSM/YTWSM who have sex with men to assess users’ comprehension of the educational content, understanding and use of intervention features, and overall impressions of app functionality.

10.1.2 Field Testing Overview

We will conduct field-testing of P3 and P3+ with 15 YMSM/YTWSM recently initiating PrEP or are PrEP non-adherent. Using an iterative process of feedback and continuing quality improvement, final app refinements and enhancements will be made to ensure full technological functionality prior to the RCT. In addition, DBS, Mitra and hair collection procedures will be assessed for feasibility and acceptability prior to the RCT.

10.1.3 RCT Overview

We will conduct a three-arm RCT to test intervention efficacy, with 240 YMSM/YTWSM initiating PrEP, recently initiated PrEP or are PrEP non-adherent. Study arms will include standard of care, P3 and P3+. The primary outcome measures are PrEP adherence measured by intracellular tenofovir-diphosphate (TFV-DP) or tenofovir alafenamide (TAF) levels and PrEP adherence measured by emtricitabine (FTC-TP) levels. Both will be obtained from whole blood specimen collected at months 3, and 6. Secondarily, we will assess the efficacy of P3/P3+ at improving PrEP adherence by analyzing self-reported PrEP use, namely weekly PrEP use and monthly PrEP use at both 3 and 6months follow-up. Additional secondary outcomes include self-reported retention in PrEP clinical

care, PrEP persistence, sexual risk behaviors, and (self-reported) STI incidence. Secondary outcome measures will be assessed at baseline, 3 and 6 months. We will also conduct a cost comparison between P3 versus P3+. As a secondary analysis, we will provide validation data on the use of hair specimens for the detection of FTC in YMSM and YTWSM at levels of 'any' and 'protective' usage.

10.2 Power Estimates

10.2.1 Usability Power Considerations

Power is not a concern for usability testing as it is performed to collect feedback from a small number of members from the target population about a preliminary version of the intervention.

10.2.2 Field Testing Power Considerations

Power is not a concern for field testing as it is performed to collect feedback from a small number of members from the target population about the functionality of the near final version of the intervention.

10.2.3 RCT Power Considerations

[figure not shown]
A total of 240 participants will be enrolled at baseline to account for a 20% expected loss to follow-up during the first 3 months of the study leaving an estimated 192 individuals (64 per arm) for analysis. Power was assessed via Monte Carlo simulation. Data were simulated as follows. A single binary baseline variable W was drawn from a Bernoulli (1/2) distribution to represent patient-level characteristics included in the analysis. A binary intervention variable A was drawn from a Bernoulli (2/3) distribution to mimic the 1:1:1 treatment allocation. A binary intermediate variable I_1 was drawn from a Bernoulli (3/4) distribution to mimic participant app utilization. A censoring variable C_1 for the month three visit was drawn from a Bernoulli (1/20) distribution, with the value 1 indicating a participant was lost-to-follow-up before the three-month visit. For uncensored participants, PrEP adherence at month three Y_1 was drawn from a Bernoulli distribution with adherence probability equal to $\text{logit}^{-1}(-1 + \beta_1 A)$. Thus, approximately 27% of participants in the SOC arm were assumed to be adherent at the three-month visit. Note that the parameter β_1 describes the log-odds-ratio of adherence comparing treatment to SOC. Next, we drew L_2 from a Bernoulli (3/4) distribution to mimic participant app utilization after the three month visit, and drew C_2 from a Bernoulli (1/20) distribution, where again a value of 1 indicated a participant was lost-to-follow-up between the three- and six-month visit. For uncensored participants, PrEP adherence at month six Y_2 was drawn from a Bernoulli distribution with adherence probability equal to $\text{logit}^{-1}(-1.5 + \beta_2 A + 1.5 Y_1)$. Thus, approximately 18% of participants in the SOC arm who were not adherent at month three, were adherent at month six, while 50% of participants in the SOC arm who were adherent at month three were again adherent at month six. Note that the parameter β_2 describes the log-odds-ratio of adherence at month six comparing treatment versus control for participants with the same month three adherence.

We generated 200 simulated data sets of 240 participants from this mechanism and analyzed each data set using longitudinal targeted minimum loss-based estimation (TMLE). This process was repeated across a range of values for (β_1, β_2) . Results for our analysis are shown in Figure 1. This figure shows power (thick black lines) as a function of (β_1, β_2) . Because the analysis is not conducted on the odds ratio scale, we have also included grid lines (gray) for the corresponding risk differences. The vertical grid lines are labeled with the value of the difference in proportion of adherent participants (P3/P3+ versus control) at month three corresponding to the particular value of β_1 . The horizontal grid lines are labeled with the value of the difference in proportion of adherent participants at month six. From the figure, we may conclude that the study has >80% power to detect a six-month treatment effect of 20% (difference in percentage adherence) even if there is no three-month effect, or conversely a

three-month treatment effect of 20% even if there is no six-month effect. In the more realistic scenario, where there is a treatment effect at both time points, we have >80% power to detect effects if the three- and six-month treatment effects are >14%.

Though the baseline and interim participant characteristics were not predictive of adherence nor of censoring, we included these characteristics in the requisite regression models for TMLE. Thus, we expect that these power calculations will be conservative for the true power if participant characteristics are informative of adherence.

Figure 1: Power as function of 3-month and 6-month adherence

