10.3.3 RCT Primary Analysis Plan

Primary Outcome: The primary analyses will assess the efficacy of the P3/P3+ intervention at 3- and 6-month follow-ups. Efficacy is defined in two ways (1) as the difference in the proportion of patients with protective levels of TFV-DP or TAF and (2) as the difference in the proportion of patients

with protective levels of FTC-TP, comparing the intervention arms to SOC. The primary tests of efficacy of the intervention (P3/P3+) will be of the following null hypotheses:

- (A1) There is no difference in the proportion of patients with protective levels of TFV-DP/TAF at 3 months.
- (A2) There is no difference in the proportion of patients with protective levels of FTC-TP at 3 months.
- (B1) There is no difference in the proportion of patients with protective levels of TFV-DP/TAF at 6 months.
- (B2) There is no difference in the proportion of patients with protective levels of FTC-TP at 6 months.

All hypotheses will be tested against the two-sided alternative of some difference in proportion. Each test will be conducted at the 0.05 level of significance and we will present corresponding 95% confidence intervals for the treatment effects.

For this analysis, we will use targeted minimum loss-based estimation (TMLE) to estimate the proportion of participants with protective levels of TFV-DP/TAF and protective levels of FTC-TP at each time and in each intervention group. TMLE is a methodology for constructing efficient and robust estimates of treatment effects and utilizes patient characteristics to account for bias due to informative participant dropout. If patient characteristics predict adherence, TMLE may also lead to greater power of tests about estimated treatment effects. Patient characteristics that will be considered in the estimation include demographic characteristics, social support, app usage and engagement, app acceptability, substance use, anxiety, and depression. We will use influence function-based variance estimators for the three- and six-month treatment effects to conduct Wald-style tests of the null hypotheses and to construct 95% confidence intervals.

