### 4.3 Hypothesis Tests and Multiple Testing Adjustment

Table 8 lists the hypotheses to be tested for each study objective. Each hypothesis comparing P3/P3+ to SOC will be tested at both 3 and 6 months, separately. For comparisons of P3 vs SOC and P3+ vs SOC, we will report the comparisons in a descriptive manner as opposed to conducting additional hypothesis tests (i.e. Secondary objectives I, II, and III).

Table 8 lists the p-value adjustment for each hypothesis test. For the primary objective no adjustment is done. For secondary objective II, a Bonferroni Correction will be applied to adjust for multiple testing and to maintain a nominal alpha level of approximately 0.05 within the objective. Due to the exploratory nature of secondary objective III, we will use a Benjamini-Hochberg adjustment, which controls the false discovery rate (FDR). We will use 0.20 as the desired FDR, which is the proportion of rejected null hypotheses that are actually true (See Glickman, 2014 for more information).

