## 6.2 Missing Data and Modification of Primary Analysis

Due to COVID-19, the collection of dry blood spots (DBS) was interrupted during this study. Therefore, the missingness in DBS will be high and it is possible for patients to have follow-up survey data, while missing the DBS follow-up data, or vice versa. Although TMLE can accommodate missingness at random (conditioned on baseline covariates) in the outcome of interest, a high amount of missing data in DBS will increase the variance of the estimator. Therefore, we decided to use survey data to “impute” the outcome variable. In doing so, we also require additional regression models to build the estimator for ATE. Please refer to the Supplement for details.

There are two survey variables that will be used to impute the values of the DBS data, namely PrEP use in the past week (number of days) and PrEP use in the past month (reported as a percentage of days). If the patient reported that they are *not* currently on PrEP, then the weekly PrEP use is assumed to be zero.

It is possible for one survey question to be present, but the other to be missing. In these cases we will use three simple forms of imputation to deal with the missing survey variable:

1. We will use mean imputation. First we stratify by current PrEP use (Y/N) and then within each group we perform mean imputation for the missing variable.
2. We will predict the survey variable (weekly or monthly PrEP use) with the other survey variable that is present using simple linear regression models
3. To impute weekly PrEP use from monthly PrEP use, we scaled the participant’s month variable to range from 0-7. Similarly to impute monthly PrEP use from weekly PrEP use, we scaled the participant’s week variable to range from 0-100.

Once this imputation is performed we can build a super learner library that includes each of the imputation methods and allow the super learner to pick the “best” methods via giving them weight in the final learner.

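### The stated power above 80% for 14-point effects does not describe the separate per-visit tests now planned (about 50-58% each), and it was simulated with 5% loss per interval where the section states 20% by month 3

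*Protocol*

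**What the plan says.** Protocol 10.2.3 gives the reason for the sample size: "A total of 240 participants will be enrolled at baseline to account for a 20% expected loss to follow-up during the first 3 months", which leaves 192 for analysis, 64 per arm. The simulation in the same section works differently: "A censoring variable C_1 for the month three visit was drawn from a Bernoulli (1/20) distribution", with another 1/20 draw between months 3 and 6. "We generated 200 simulated data sets of 240 participants from this mechanism", and each was analysed by longitudinal TMLE. The simulated covariates predicted neither adherence nor censoring.

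Two conclusions are drawn. Power exceeds 80% for a 20-point effect at one visit with none at the other. For effects at both visits, "we have >80% power to detect effects if the three- and six-month treatment effects are >14" percent. The section does not say which test was simulated. On the axes of Figure 1 it says: "The horizontal grid lines are labeled with the value of the difference in proportion of adherent participants at month six".

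Protocol 10.3.3 lists four primary null hypotheses, one for each of two markers at each of two visits, against two-sided alternatives: "Each test will be conducted at the 0.05 level of significance". SAP 4.3 agrees: "Each hypothesis comparing P3/P3+ to SOC will be tested at both 3 and 6 months, separately", with no multiplicity adjustment for the primary objective. SAP 6.2 adds, on the blood samples that supply the primary outcome: "Therefore, the missingness in DBS will be high".

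**The concern.** Two things in the power section do not fit the rest of the plan.

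First, the loss assumption contradicts itself. A trial sized to absorb 20% loss should have its power evaluated at about 192 participants, but the simulation evaluates it at about 228 at month 3 and 217 at month 6.

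Second, the 14-point figure has no named test, and it is not the power of any of the four hypotheses listed. The SAP revision history records that separate tests replaced a joint test of no effect at both visits. That may explain the mismatch, but the point rests only on the current text.

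This is the protocol's only power statement for the primary outcomes. A reader who takes it at face value would treat a null result at one visit as fairly strong evidence against a 14-point benefit. If each test has about 50% power at that effect, a null is as likely as not even when the benefit is real.

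**Working it through.** **Inputs, all from Protocol 10.2.3.** N = 240; treatment A ~ Bernoulli(2/3), that is P3 and P3+ pooled against standard of care (SOC); month-3 adherence probability expit(−1 + β₁A); month-6 probability expit(−1.5 + β₂A + 1.5Y₁). Because the simulated covariates carry no information, unadjusted differences with influence-function variances stand in for TMLE.

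**SOC rates.**
- Month 3: expit(−1) = 0.269.
- Month 6: 0.731 × 0.182 + 0.269 × 0.500 = 0.268.

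**Expected numbers with data.**
- As simulated: 240 × 0.95 = 228 at month 3; 228 × 0.95 = 216.6 at month 6.
- As stated: 240 × 0.80 = 192 at month 3. With a further 5% loss, 192 × 0.95 = 182.4 at month 6.

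**Can the published figure be reproduced?** The month-6 difference depends on both β₁ and β₂, because the treatment effect on Y₁ carries forward. One label per horizontal grid line is therefore not enough to fix it. Two readings of 14 points at both visits are possible:
- *True 14-point differences at both visits:* β₁ = 0.632, β₂ = 0.473.
- *Month-6 label computed at β₁ = 0:* β₂ = 0.707. With β₁ = 0.632 the actual month-6 difference is 0.591 × 0.3115 + 0.409 × 0.6697 − 0.268 = 0.190, or 19 points.

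Simulated power, two-sided 0.05, 20,000 replicates (results vary by up to about 1 point between runs):

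| Reading and loss | Month-3 test | Month-6 test | Either visit | Joint 2-df test |
|---|---|---|---|---|
| True 14/14, 5% per interval | 58% | 56% | 77% | 66% |
| True 14/14, 20% by month 3, then none | 51% | 51% | 71% | 60% |
| True 14/14, 20% then 5% | 51% | 50% | 70% | 58% |
| Label at β₁ = 0, 5% per interval | 58% | 80% | 88% | 80% |
| Label at β₁ = 0, 20% then 5% | 52% | 74% | 83% | 74% |

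So about 80% comes back from a joint two-visit test at 5% loss, if the month-6 label was computed at β₁ = 0. That reading is an inference, since Figure 1 is not reproduced. With true 14-point differences at both visits, none of these tests reaches 80%. Month-3 power is 51-58% on either reading.

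**Closed-form check of one test.** SE = √[p₁(1−p₁)/(2n/3) + p₀(1−p₀)/(n/3)], with p₀ = 0.269, p₁ = 0.409 and power Φ(0.14/SE − 1.96).
- n = 228: SE = √(0.2417/152 + 0.1966/76) = 0.0646; power Φ(0.21) = 58%.
- n = 192: SE = √(0.2417/128 + 0.1966/64) = 0.0704; power Φ(0.03) = 51%.
- n = 182.4: SE = 0.0723; power 49%.

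The difference with 80% power per test is 18.2 points at n = 228, 19.8 at n = 192 and 20.4 at n = 182.

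**The 20-point single-visit claim.** Per-test power is 85% (month 3) and 84% (month 6) at 5% loss. At 20% loss it is about 79% at month 3 and 77-80% at month 6. The closed form at n = 192 gives 81%.

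**Covariate gain needed for 80% at 14 points.** The SE must be 0.14/(1.960 + 0.842) = 0.0500. The required variance reduction is 1 − (0.0500/0.0704)² = 50% at n = 192, and 1 − (0.0500/0.0646)² = 40% at n = 228. A 20% reduction at n = 192 gives SE 0.0630 and about 60% power.

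**Simulation error.** With 200 replicates near 80%, the 95% margin is 1.96 × √(0.8 × 0.2/200) = 5.5 points.

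**The case against.** The strongest reply is that the protocol never claims 80% power for each visit's test; it speaks of detecting effects when both are present. If that means rejection at one or more visits, the separate tests give 77% at 14 points and 81% at 15 under 5% loss. This is close to the stated figure given the 200 replicates. The reading is possible, but it carries about 10% type I error across the two visits, drops to about 70% and 75% at the section's own 20% loss, and gives no power for any listed hypothesis. It strengthens the case for naming the test.

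A second reply is that the planned estimator is not an unadjusted comparison. It adjusts for baseline blood level, PrEP use, age, site and race/ethnicity, and it brings in self-report where blood data are missing. That is correct, and it is why the figures here are described as unadjusted. The protocol's own simulation assumed no covariate gain, however, so the comparison with its stated figure is like for like. Neither document supports a 40-50% variance reduction.

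Third, the documents cannot show whether 1/20 was the loss actually simulated or a slip in the write-up. Either way the text must be reconciled, and this part accounts for only about 5-7 points per test.

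Finally, SAP 6.1 lists the analysis as done in April 2022, so a revised figure changes no result and precision will be read from the confidence intervals. This limits the consequence to how a null is interpreted and how the design is reported.

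**Conclusion.** The concern holds and should be fixed. The loss conflict is plain within Protocol 10.2.3. The 14-point power statement does not apply to the tests specified in Protocol 10.3.3 and SAP 4.3: each has about 56-58% power at the simulated loss and about 50% at the stated loss, against the more than 80% reported. These figures assume the protocol's own adherence model, a true 14-point marginal difference at both visits and no gain from covariates. The explanation through the grid label and a joint test is inferred; neither the loss conflict nor the month-3 shortfall depends on it. The 20-point single-visit statement survives at 5% loss and is borderline at 192 participants. The high blood-sample missingness expected in SAP 6.2 would lower power, while adjustment and the self-report data may raise it. The documents quantify none of these.

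**What to change.** In Protocol 10.2.3:

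1. State one loss assumption: 20% by month 3, plus the further loss expected by month 6.
2. Re-run the simulation with separate two-sided 0.05 tests at each visit, as in SAP 4.3. Define the month-6 difference marginally and use several thousand replicates.
3. Name the test behind every power figure.
4. Replace the 14-point sentence with the result. Before any covariate gain, expect about 50% power per test at 14 points and about 80% at 20 points. Say that power is lower if blood-sample missingness exceeds 20%; the unadjusted closed form at 30% missing (n = 168) gives 46% and 75%. Any gain claimed from covariates or self-report should be simulated under a stated assumption.

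Other SOC adherence rates are an optional sensitivity case. The cost is one simulation re-run and a reworded paragraph. Sample size, estimand, tests and estimates do not change; the stated power becomes less favourable.

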1.0 INTRODUCTION

1.1 Background

Between 2002 and 2011, rates of new HIV infections declined by more than 30% overall in the United States (US) but increased by 132% among young men who have sex with men (YMSM) ages 13-24.¹ Regional studies suggest that HIV prevalence among transgender women (TW) are among the highest of all risk groups, especially TW of color, and African-American TW in particular.²⁻⁴ Despite overwhelming scientific evidence of the efficacy and safety of pre-exposure prophylaxis (PrEP) to prevent HIV infection in YMSM and young transgender women who have sex with men (YTWSM)

efficacy in all PrEP studies has been strongly correlated with drug levels, and drug monitoring indicates that adherence has been suboptimal in a substantial proportion of participants.⁵⁻⁷ Adherence to medications, including PrEP, is known to be a significant challenge for adolescents and young adults.⁸⁻¹⁴ in a recent study of PrEP use among 200 YMSM (mean age 20.2 years, 54.5% Black, 26.5% Latino) at week 4, 56% had protective levels of intracellular tenofovir-diphosphate (TFV-DP) (i.e., consistent with ≥ 4 pills/week). This decreased to 48% at week 24 and 34% at week 48. PrEP adherence rates were lower among African American YMSM and below the protective threshold at all-time points measured.¹⁴ To date, there are no proven interventions for YMSM and YTWSM to promote consistent and persistent PrEP adherence. Interventions that improve PrEP adherence are urgently needed to maximize HIV prevention benefits for YMSM and YTWSM.

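### The stated >80% power for a 20-point effect was simulated with 5% loss per visit and an unexplained 27% SOC adherence rate; with the section's own 20% loss it is about 75% to 81% over SOC rates of 27% to 56%

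*Protocol*

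**What the plan says.** Protocol section 10.2.3 enrols 240 and allows for 20% loss in the first three months, leaving 192 for analysis (64 per arm). It then describes a simulation of 240 participants in which censoring is 1 in 20 before month 3 and a further 1 in 20 between months 3 and 6. In it, "approximately 27% of participants in the SOC arm were assumed to be adherent at the three-month visit". For month 6, "approximately 18% of participants in the SOC arm who were not adherent at month three, were adherent at month six", as were half of those adherent at month 3. From 200 data sets per setting the section concludes that there is ">80% power to detect a six-month treatment effect of 20% (difference in percentage adherence) even if there is no three-month effect". It makes the same claim with the two visits exchanged.

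Section 1.1 gives the only numerical protective-level rates in the protocol, from a study of 200 young MSM: 56% at week 4, after which "This decreased to 48% at week 24 and 34% at week 48". Section 10.3.3 plans two-sided Wald-style tests of each marker at each visit: "Each test will be conducted at the 0.05 level of significance".

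**The concern.** Two inputs to the power figure do not agree with the rest of the protocol. The loss simulated (5% per visit) is much smaller than the loss planned for (20% by month 3). The SOC rate is unsourced and lies below every rate quoted in the background. For a difference in proportions, the variance is largest near 50%, so 27% is a favourable choice under an unpooled Wald test. If power at the planned numbers is below the stated figure, a null result would be read against more assurance than the design gives.

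**Working it through.** **Inputs.** Difference of 20 points; two-sided 0.05 at each visit (10.3.3); SOC against pooled P3/P3+ in a 1:2 ratio. SOC rate in the simulation: logit⁻¹(−1) = 26.9% at month 3; at month 6 with no effect, 0.731 × 18.2% + 0.269 × 50% = 26.8%. Cited rates: 34%, 48%, 56% (1.1). Retained numbers:

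- 20% loss: 240 × 0.80 = 192, or 64 v 128.
- 5% loss, month 3: 240 × 0.95 = 228, or 76 v 152.
- a further 5%, month 6: 228 × 0.95 = 216.6, or about 72 v 144.

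**Formulas.** With p1 = p0 + 0.20 and SE = √[p0(1−p0)/n0 + p1(1−p1)/n1]:

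- Unpooled (nearest simple form of the planned Wald test): power ≈ Φ(0.20/SE − 1.96).
- Pooled: power ≈ Φ[(0.20 − 1.96·SE0)/SE], where SE0 = √[p̄(1−p̄)(1/n0 + 1/n1)] and p̄ = (p0 + 2p1)/3.

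**The plan's own figure.** At 26.9% SOC with 5% loss per visit, unpooled power is 86.8% (month 3) and 85.1% (month 6); pooled, 84.1% and 82.2%. A 20,000-replicate simulation of the section's mechanism, with unadjusted tests, gives 85.6% and 83.4%. The >80% claim therefore reproduces on its own inputs. The power text does not name the test. If it was a joint two-visit test (an assumption), the simulated power is 82.1% for a month-3 effect only and 80.0% for a month-6 effect only.

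**At the planned 64 v 128, SOC 26.9%.**

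- SE = √(0.269 × 0.731/64 + 0.469 × 0.531/128) = √(0.00307 + 0.00195) = 0.0708. Then 0.20/0.0708 = 2.82, and Φ(2.82 − 1.96) gives 80.6%.
- Pooled: p̄ = 0.402, SE0 = 0.0751, (0.20 − 0.1471)/0.0708 = 0.746, giving 77.2%.

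**All settings** (power in %, unpooled / pooled):

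| SOC rate | 64 v 128 | 76 v 152 | 72 v 144 |
|---|---|---|---|
| 26.9% | 80.6 / 77.2 | 86.8 / 84.1 | 85.1 / 82.2 |
| 34% | 77.3 / 75.2 | 84.0 / 82.2 | 82.1 / 80.2 |
| 48% | 76.2 / 76.4 | 83.0 / 83.1 | 81.0 / 81.2 |
| 56% | 78.6 / 80.2 | 85.1 / 86.3 | 83.3 / 84.6 |

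Between 34% and 48% the lowest values, both pooled and near 38% to 39%, are 74.8% at 64 v 128 and 79.8% at 72 v 144.

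**Separating the two causes.**

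- Loss, SOC held at 26.9%, month 3: 86.8 − 80.6 = 6.2 points unpooled; 84.1 − 77.2 = 6.9 pooled. Simulating the section's mechanism with 20% loss by month 3 and 5% after gives 79.3% at month 3 and 77.0% at month 6, against 85.6% and 83.4%.
- SOC rate, 64 v 128 held fixed, unpooled: drops of 3.3, 4.4 and 2.0 points at 34%, 48% and 56%, with a maximum of 4.7 at 41% (75.9%). Pooled, power moves from 77.2% to between 75.2% and 80.2%, so it can rise.
- SOC rate with the simulated 5% loss kept: 80.2% to 86.3% at the three cited rates.

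**Difference detectable with 80% power at 64 v 128.** Unpooled: 19.8 points at 26.9%, and 20.7, 20.9 and 20.3 at 34%, 48% and 56%. Pooled: 20.7, 21.2, 20.9 and 20.0.

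**Simulation error.** With 200 data sets the standard error at 80% power is √(0.8 × 0.2/200) = 2.8 points; with 2,000 it is 0.9.

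**The case against.** A reader might infer that moving the SOC rate from 27% to the cited rates is what takes power below 80%. The documents do not support that. The >80% figure was simulated on 240 participants with 5% loss per visit; changing only the SOC rate there leaves single-visit power above 80% at all three cited rates. The shortfall needs the 20% loss as well, and under the pooled formula 64 v 128 is already below 80% at 27%.

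The cited rates are also an imperfect benchmark. They concern TFV-DP only and a cut-off of at least 4 pills a week, whereas section 2.1 asks for more than 4 doses and includes FTC-TP, for which no rate is cited. None falls at month 3, and week 48 is beyond the last visit. Section 1.1 reports lower adherence among African American young MSM without a figure, and sections 3.1, 4.3 and 10.1.3 include non-adherent youth in the target group. On the other side, section 4.1 admits anyone on PrEP with an active prescription, and week 24 (48%) is close to month 6. These points call for a range of SOC rates; they do not justify 27% alone.

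Section 10.2.3 also says its figures are conservative if participant characteristics predict adherence, and SAP section 4.2 adjusts for baseline DBS and PrEP use, age, site and race/ethnicity. That stands. At 64 v 128 the unpooled ratio 0.20/SE is 2.71, 2.67 and 2.75 at 34%, 48% and 56%, against the 2.80 needed for 80%. A variance reduction of 1 − (ratio/2.80)², about 3% to 9%, would close the gap. The documents do not say what reduction to expect.

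Finally, treatment effects will be reported with confidence intervals, and SAP section 6.1 dates the analysis to April 2022. The correction therefore bears on how the results are read, not on how the trial is run.

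**Conclusion.** The concern holds in a modest form. At the section's planned numbers, unadjusted power for a 20-point difference at one visit is about 77% to 81% at the assumed 27% SOC rate and about 75% to 80% at 34% to 56%, instead of clearly above 80%. Loss is the larger cause (about 6 to 7 points at month 3); the SOC rate adds about 2 to 5 under the unpooled formula. If a further 5% is lost after month 3, simulated month-6 power is 77.0% at 27% SOC and between 73.5% and 74.9% at SOC rates of 34% or 48%.

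This rests on separate per-visit tests at 0.05, unadjusted normal approximations, and the protocol's own 64 v 128. It does not show that the SOC rate alone defeats the claim, that 34% to 56% is the correct range for this trial's endpoint, or that more participants were needed: the difference detectable with 80% power stays at roughly 20 to 21 points.

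**What to change.** Re-run the section 10.2.3 simulation with the stated 20% loss by month 3, the planned separate test at each visit, SOC rates of 27%, 34%, 48% and 56%, and at least 2,000 data sets per setting. State what loss is assumed after month 3. Replace the single >80% claim with the resulting range: expect about 75% to 81% unadjusted at 64 v 128, with 80% power for roughly 20 to 21 points, and somewhat lower power at month 6 if further loss is included. Say that the cited rates use at least 4 pills a week and TFV-DP only, that covariate adjustment may raise power by an amount not quantified, and why 27% is used if it is kept.

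The cost is a short re-run and a few sentences. Enrolment and the analysis do not change; the only downside is a slightly less favourable stated power.
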